- 1. Population: Adult participants with AML who are in CR after aHSCT and are at high risk of relapse defined as positive MRD any time at ≥ Day 60 after aHSCT (with a confirmed MRD positivity at least 2 weeks after systemic immunosuppression has been tapered off) and who are exposed to study treatment for at least 2 cycles (minimum exposure criterion defined in Section 12.1) or who experienced a DLT within the DLT observation period.
- 2. Primary variable: Proportion of adult participants who experience at least one dose limiting toxicity (DLT) (see Table 6-2) including but not limited to aGvHD and cGvHD as per investigator assessment between Cycle 1 Day 1 (first administration of sabatolimab) and end of Cycle 2 (Day 28).
- 3. Treatment of interest: Treatment with sabatolimab as monotherapy at 400 mg and 800 mg Q4W dose levels taken for the entire study duration post aHSCT.
- 4. Handling of remaining intercurrent events:
 - Delay to start Cycle 3 due to any reason: a DLT that will occur after Day 28 of Cycle 2 and before starting Cycle 3 will be considered in the analysis (treatment policy strategy).
 - Failure to start Cycle 3 due to any reason: a DLT that will occur up to the theoretical last day of Cycle 2 (Cycle 2 Day 28) will be considered in the analysis regardless of permanent discontinuation after the dose of sabatolimab in Cycle 2 (treatment policy strategy).
- 5. Summary measure for the primary safety estimand is the proportion of participants with treatment-emergent dose limiting toxicity as per investigator assessment reported during the first 2 cycles.

The **primary efficacy estimands for adult participants** included in this study are described by the following attributes:

- 1. Population: Adult participants with AML who are in CR after aHSCT and are at high risk of relapse defined as positive MRD at baseline any time at ≥ Day 60 after aHSCT (with a confirmed MRD positivity at least 2 weeks after systemic immunosuppression has been tapered off).
- 2. Primary variable: Proportion of adult participants who remain with no evidence of hematologic relapse (no evidence of any of the following: bone marrow blasts ≥5%; reappearance of leukemic blasts in the blood; or development of extramedullary disease) as per investigator assessment after 6 cycles of the study treatment.

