If the study treatment (sabatolimab + azacitidine) is interrupted for toxicities other than GvHD and the start of the subsequent study treatment cycle is delayed for more than 28 consecutive days from the intended start date of cycle (Day 29 of the previous cycle) the participant should be discontinued from study treatment. For permanent discontinuation of study treatment due to acute and/or chronic GvHD, refer to Table 6-4.

Permanent discontinuation of only one component sabatolimab (or azacitidine - Combination cohort)

If **one component only** of the study treatment (azacitidine or sabatolimab) is discontinued for toxicities (other than GvHD), then the treatment may continue with the other component of study treatment alone (sabatolimab alone or azacitidine alone) as long as the participant benefits per investigator's judgement.

These dose changes must be recorded on the appropriate CRF.

^{**}Per investigator judgement

Table 6-4 Criteria for dose interruption, re-initiation and discontinuation of study treatment due to GvHD

	y treatment due to G	T	Diagontino ()				
	Interrupt study treatment [£] (sabatoli mab monotherapy or in combination with azacitidine)	Resume study treatment (sabatolimab monotherapy or in combination with azacitidine)	Discontinue study treatment permanently (sabatolimab monotherapy or in combination with azacitidine)				
Acute GvHD (aGvHD)	New onset grade II requiring systemic therapy New onset grade III Baseline grade I or II worsening to grade III III III III III III III II	 If aGvHD improved to ≤ grade I or to baseline prior to starting study treatment within ≤ 8 weeks of observation from onset or exacerbation of aGvHD The following are allowed at time of resumption of study treatment: Topical, nonabsorbable or inhaled steroids Systemic doses of steroids ≤ 10 mg prednisone or equivalent Tacrolimus with trough levels <5 ng/mL OR CSA with trough levels <200 ng/mL (indicating continuous IST taper) 	 Grade IV aGvHD Recurrence or exacerbation of aGvHD to ≥ grade III after resuming study treatment Steroid-refractory aGvHD No improvement to ≤ grade I or to baseline prior to starting study treatment after 8 weeks of observation from onset or exacerbation of aGvHD 				

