- Participant has experienced a DLT within the DLT observation period from first dose of sabatolimab to the end of Cycle 2.

Note: For a participant with a grade 4 neutropenia, thrombocytopenia and pancytopenia (hematological toxicity that could be qualified as a DLT) occurred during the DLT evaluation period (from Cycle 1 Day 1 to the end of Cycle 2), a sufficient follow-up time will be considered to determine if the adverse event has to be qualified as a DLT.

Note: The period from Cycle 1 Day 1 to the day before Cycle 3 Day 1 corresponds to the period from the first dose of sabatolimab in Cycle 1 to the day before the first dose of sabatolimab in Cycle 3. In case of Cycle 3 is not initiated, the period to consider for the DLT evaluation will be the period from the first dose of sabatolimab in Cycle 1 to the theoretical last day of Cycle 2 (Cycle 2 Day 28).

Pharmacokinetic Analysis Sets

The sabatolimab pharmacokinetic analysis sets include all participants from the Safety Set who provide at least one evaluable sabatolimab PK concentration.

For a concentration to be evaluable:

- Dosing information must be properly documented (data and time of administration)
- For post-dose samples: planned dose of sabatolimab must be taken prior to sampling
- For pre-dose samples: the sample is collected before the next dose administration

Participant Classification

Participants may be excluded from the analysis populations defined above based on the protocol deviations entered in the database and/or on specific participant classification rules defined in Table 2-1.

Analysis set	Protocol deviations leading to exclusion	Non protocol deviation leading to exclusion
FAS	No written informed consent for participation in the study	No dose of any component of study treatment
Safety Set	No written informed consent for participation in the study	No dose of any component of study treatment
DDS	No written informed consent for participation in the study	Did not met the minimum exposure criterion or no sufficient safety evaluations in the absence of DLT during the DLT evaluation period
Sabatolimab-PK analysis set	No written informed consent for participation in the study	See definition of PK analysis sets

Table 2-1Participant classification based on protocol deviations and non protocoldeviations criteria

Withdrawal of Informed Consent

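### Between Cycle 2 Day 28 and Cycle 3, whether a DLT counts depends on whether Cycle 3 later starts, so in that interval GvHD that ends treatment can never enter the primary safety endpoint

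*Protocol*

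**What the plan says.** Protocol 2.1 defines the adult safety variable as at least one DLT from the first sabatolimab dose to the end of Cycle 2, and adds two intercurrent-event rules, both labelled treatment policy.

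- Cycle 3 delayed: "a DLT that will occur after Day 28 of Cycle 2 and before starting Cycle 3 will be considered in the analysis".
- Cycle 3 never started, whatever the cause: "a DLT that will occur up to the theoretical last day of Cycle 2 (Cycle 2 Day 28) will be considered in the analysis". This applies even when treatment was stopped for good once the Cycle 2 dose had been given.

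The adolescent estimand has the same two rules, and SAP 1.2.1 repeats both sets. The note on the Dose-Determining Set (DDS) in SAP 2.2 leaves no room for another reading. When Cycle 3 does start, the window runs "to the day before the first dose of sabatolimab in Cycle 3". For participants who never reach that cycle, the note has a separate sentence: "In case of Cycle 3 is not initiated, the period to consider for the DLT evaluation will be the period from the first dose". That period closes at the theoretical Cycle 2 Day 28. The only allowance for later information is for grade 4 cytopenias, for which "a sufficient follow-up time will be considered to determine if the adverse event has to be qualified as a DLT". It applies to cytopenias that occur inside the window, not to events that begin after it.

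**The concern.** Under a treatment policy strategy, stopping treatment should not change which events are counted. Here the extension past Day 28 is given only to participants who go on to receive Cycle 3. A DLT in that interval is therefore selected by its own consequence: it counts if the participant recovers enough to be re-dosed and is dropped if it ends treatment.

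This selection is tied to severity. Protocol Table 6-4 lists "Grade IV aGvHD", severe chronic GvHD and moderate chronic GvHD of the lungs under permanent discontinuation, and all three are DLT criteria in Table 6-2. Severe GvHD is the study's principal safety concern, and Protocol 4.1 says that onset of GvHD or immune-related events may be delayed. The adult DLT endpoint is still selected for the final report in SAP Table 1-1.

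**Working it through.** **1. Same interval, two outcomes.** With no earlier delay, Cycle 2 Day 28 is study Day 56 (2 × 28) and Cycle 3 Day 1 is Day 57. Take two participants with two full infusions, no earlier DLT, and a DLT-criteria event that begins after Day 56 and before any Cycle 3 dose.

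- A: the event resolves and Cycle 3 starts late. Counted.
- B: grade IV acute GvHD, treatment stopped under Table 6-4. Not counted.

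Participant B can stay in the DDS as an evaluable non-DLT, because Protocol 12.1 asks only for two full-dose infusions and 28 days of observation after the second. The numerator loses the event and the denominator keeps the person.

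A prior treatment hold is not strictly needed. Under Protocol 8.4.4, GvHD is assessed every two weeks in Cycles 1 and 2 and then on Day 1 of each cycle. After Cycle 2 Day 15 the next scheduled assessment is therefore Cycle 3 Day 1. An event with recorded onset at that visit, before dosing, falls in the gap if it ends treatment.

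**2. Reproducing the plan's model.** Inputs from Protocol Appendix 16.6:

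- logit π(d) = log α + β·log(d/800)
- log α ~ N(logit 0.15, SD 2) and log β ~ N(0, SD 1)
- recommended dose = the highest dose with P(π ≥ 0.50) < 0.25

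Numerical integration on a grid gives prior P(π ≥ 0.50) of 0.103 at 400 mg and 0.194 at 800 mg, against 0.103 and 0.194 in Table 16-10. The data scenarios at the 50% threshold in Table 16-11 also reproduce. The probability shown is for the recommended dose.

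| DLTs | Plan: dose, P | Re-run: P |
|---|---|---|
| 1/6 | 800, 0.125 | 0.131 |
| 2/6 | 400, 0.094 | 0.098 |
| 2/8 | 800, 0.216 | 0.222 |
| 3/8 | 400, 0.129 | 0.132 |
| 0/6 + 4/9 | 800, 0.134 | 0.134 |
| 0/6 + 5/9 | 400, 0.005 | 0.005 |
| 1/6 + 4/9 | 800, 0.184 | 0.187 |
| 1/6 + 5/9 | 400, 0.036 | 0.035 |

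The recommended doses agree and the probabilities are within 0.01.

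**3. Adding one uncounted event.**

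| Counted → with one more | Dose examined | P(DLT rate > 50%) | Model recommendation |
|---|---|---|---|
| 1/6 → 2/6 | 800 mg | 0.131 → 0.339 | 800 → 400 |
| 2/6 → 3/6 | 400 mg | 0.098 → 0.319 | 400 → stop |
| 2/8 → 3/8 | 800 mg | 0.222 → 0.428 | 800 → 400 |
| 0/6 + 4/9 → 0/6 + 5/9 | 800 mg | 0.134 → 0.322 | 800 → 400 |
| 1/6 + 4/9 → 1/6 + 5/9 | 800 mg | 0.187 → 0.381 | 800 → 400 |

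**4. Illustrative range.** The documents give no rate for such events. Assume that a fraction u of DLTs is missed this way while the participants stay in the denominator, so each true rate p becomes p(1 − u). With true rates of 40% and 50%, averaging over cohort sizes 6–8 and 9–12 (the plan does not state its mix), the model's selection probabilities are:

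| u | 400 mg | 800 mg | stop |
|---|---|---|---|
| 0 | 0.507 | 0.109 | 0.384 |
| 10% | 0.515 | 0.183 | 0.302 |
| 20% | 0.493 | 0.281 | 0.226 |
| 30% | 0.443 | 0.397 | 0.160 |

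At u = 0, Table 16-12 gives 0.496, 0.127 and 0.377, within 2 percentage points. The values of u are assumptions, not estimates.

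**The case against.** The declared variable ends at Cycle 2 Day 28. Every treatment-stopping DLT up to that day counts, and a participant who never starts Cycle 3 has the same nominal window as one who starts on time. Only late starters gain an extension, and it can only add events. All of this stands. A reader might infer that the worst toxicities are generally left out, or that the sickest participants have the shortest window. The documents do not support that: the gap is confined to onset after Day 28, in participants without an earlier DLT who never receive Cycle 3. But once the plan counts some post-Day-28 events in the endpoint, it needs a rule for which ones that does not depend on recovery.

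Late events also reach other reviews. SAP 2.10 gives the safety review meetings DLTs and adverse events up to the data cut-off. Protocol 6.5.2 bases dose decisions on all relevant data, including GvHD, with the model only as a guide. SAP 2.7.1 tabulates adverse events over the overall safety period, to 150 days after sabatolimab. This limits the harm to the DLT proportion and the model input. It is not complete cover. If the last dose is on nominal Day 29, the on-treatment period ends on Day 59 (29 + 30), so a later event misses the on-treatment tables. In addition, SAP Table 1-1 does not select the GvHD incidence endpoint for the final report.

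Finally, the dose decisions are past. Recruitment stopped in December 2023, and an adolescent was enrolled in Part 2, which opens to adolescents only after the run-in. The adolescent analysis is itself not assessable (SAP 2.5.1). This also stands. The step 3 shifts show how sensitive the model is. They are not evidence that a wrong dose was chosen, and the documents do not support that inference.

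**Conclusion.** The concern holds within narrow limits. For DLTs that begin after Cycle 2 Day 28 and before any Cycle 3 dose, inclusion depends on a later outcome. Where Table 6-4 is followed, three GvHD criteria can never count in that interval. Against any common window that runs past Day 28, the error is towards understating toxicity. Its size is unknown and may be zero, because the number of participants affected is not stated. What makes it worth correcting is the cohort size: 6 to 8 and 9 to 12 evaluable participants, where one event can move the model across its 0.25 limit (0.13 to 0.34 for 1/6 to 2/6). The remaining consequence is for the adult DLT proportion and posterior in the final report, not for dose selection.

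**What to change.** Reconcile the two intercurrent-event rules in Protocol 2.1 and SAP 1.2.1 with the note in SAP 2.2, so that the end of the counting window does not depend on whether or why Cycle 3 starts. Use one calendar end for all participants. Its length is for the sponsor to set. For the final report:

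- recompute the adult DDS DLT proportion and the BLRM posterior on that window;
- list every event meeting DLT criteria with onset after Cycle 2 Day 28 in participants who never started Cycle 3.

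The cost is a few sentences and a small re-run. Adverse events are already followed to 150 days after sabatolimab, but a few late events may need a DLT determination made retrospectively, since none was required outside the window. The DLT proportion may become slightly less favourable. It cannot fall if the common end is no earlier than the latest DLT now counted. An earlier end would also remove the asymmetry, but could drop events that count today, so the list should be given whichever length is chosen.

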2.2 Secondary estimands

Not applicable.

3 Study design

This is a Phase Ib/II open label, multi-center study of sabatolimab, as monotherapy and in combination with azacitidine, in participants with AML/secondary AML who have received one aHSCT and who are in CR (bone marrow blasts < 5% and no extramedullary disease) but MRD+, any time at ≥ Day 60 after aHSCT (MRD positivity confirmed at least 2 weeks after immunosuppressive medications tapered off).

Study treatment will be administered in 28-day treatment cycles. The study will enroll a total of approximately 59 participants [20 participants in safety run-in (Cohorts 1 and 2), 13 in sabatolimab monotherapy expansion cohort (Cohort 4), 20 in the combination cohort (Cohort 3), 6 in the adolescent cohort (Cohort 5)] and will be conducted in two parts (Figure 3-1).

Part 1 is a Safety Run-in to assess whether sabatolimab is safe in the post-aHSCT setting when administered as a single agent at two dose levels, 400 mg and 800 mg, on a Q4W regimen on Day 1 of every 28-day cycle. Sabatolimab has been demonstrated to be safe and well tolerated as a single agent and in combination with HMAs in previous studies. However, sabatolimab has not been explored in the post-aHSCT setting; therefore, the principal assessment of safety will be based on the rate of unacceptable level of toxicity [ie, treatment-emergent dose limiting toxicities (DLTs) including but not limited to aGvHD and cGvHD during the first 2 cycles of study treatment (Table 6-2).

A total of approximately 20 participants will be enrolled to Part 1 across the two dose levels. Approximately 8 participants will be enrolled at the starting dose level, 400 mg Q4W IV in order to obtain at least 6 evaluable participants. If the observed DLTs rate does not exceed the acceptable threshold at this starting dose, then approximately 12 participants will be enrolled in a second cohort of Safety Run-in and treated with sabatolimab monotherapy at dose level 800 mg Q4W in order to obtain at least 9 evaluable participants. For each dose level, once the required number of evaluable participants has been confirmed, enrollment will be halted until participants have completed the DLT observation period (\geq 56 days following the first dose) (Section 6.5.3). If no safety concerns were identified at either sabatolimab dose level, the preferred dose level for sabatolimab will be 800 mg IV Q4W.

Part 2 will assess efficacy as well as safety, PK, and MRD status when sabatolimab is administered at the recommended dose for expansion determined in Part 1 as monotherapy and/or in combination with azacitidine. Part 2 will enroll a total of approximately 13 participants in the monotherapy expansion [to obtain a total of 25 participants from the combined Safety Run-in (Cohort 2) and monotherapy expansion cohort (Cohort 4)]; and 20 participants in the combination cohort (Cohort 3). Participants will be randomized to one of these two cohorts in Part 2 - combination cohort (Cohort 3) or monotherapy expansion cohort (Cohort 4) - and the randomization ratio will depend on the number of participants from the Safety-Run in part (Part 1) already treated with sabatolimab at the selected dose level for expansion (See Section 6.3.2).

In the monotherapy expansion cohort (Cohort 4), sabatolimab will be administered as a single agent on Day 1 (Q4W) of every 28-day cycle.

In the combination cohort (Cohort 3) of sabatolimab with azacitidine, sabatolimab will be administered on Day 5 (+3 days) of every 28-day cycle IV on a Q4W regimen.

[figure not shown]
Azacitidine will be administered IV or SC at 50 mg/m² on Days 1 to 5 for 5 days per cycle. In the combination cohort (Cohort 3), participants unable to tolerate one of the study drugs may continue on study receiving only the tolerated study drug.

In addition, based on Part 1 Safety Run-in results, an additional cohort of 6 adolescent participants (Cohort 5) will be opened (if no unacceptable rate of toxicities is observed in adults) to include participants who are 12 years or older but less than 18 years old and meet eligibility for this study. This cohort will be conducted in aHSCT site(s) that treat participants at this age group.

The decision to open the combination cohort (Cohort 3) and the adolescent cohort (Cohort 5) will be based principally on safety data obtained in Part 1. The decision to open the sabatolimab monotherapy expansion cohort (Cohort 4) will be based on an overall assessment of available safety, preliminary response assessment, PK, and MRD assessments.

Throughout the study, the decision whether or when to open an additional cohort(s) will be based on the overall safety, PK, tolerability, and preliminary response assessment.

Figure 3-1 Study design

Page 34 of 153 Protocol No. CMBG453F12201

Study treatment will be administered for up to a maximum of 24 cycles or until a participant experiences hematologic relapse (bone marrow blasts ≥5%; or reappearance of blasts in the blood; or development of extramedullary disease) as defined by ELN 2017 (Döhner et al 2017); or unacceptable toxicity, whichever is earlier. For participants who achieve negative MRD and maintain MRD negativity for 12 consecutive cycles, study treatment (sabatolimab monotherapy or sabatolimab in combination with azacitidine) may be discontinued earlier at investigator's discretion.

In each cohort, response status will be evaluated by standard hematologic/morphologic criteria per investigator's assessment after each cycle up to Cycle 3, then after every 3 cycles of study treatment up to cycle 12, and then after every 6 cycles for up to a total of 24 cycles (post cycle 1, 2, 3, 6, 9, 12, 18, 24).

For participants with MRD+ centrally assessed at baseline (defined as at time of enrollment prior to starting treatment), MRD status will be evaluated by Novartis central laboratory at the same schedule as the hematologic/morphologic disease assessment after cycles 1, 2 and 3 and then after every 3 cycles of study treatment up to cycle 12, and then after every 6 cycles for up to a total of 24 cycles (post cycle 1, 2, 3, 6, 9, 12, 18, 24). In addition, MRD status will be assessed locally at the same schedule as the hematologic/morphologic disease assessment after cycles 1, 2 and 3 and then after every 3 cycles of study treatment up to cycle 12, and then after every 6 cycles for up to a total of 24 cycles (post cycle 1, 2, 3, 6, 9, 12, 18, 24).

After completion of the treatment period, all participants will enter post-treatment followup until hematologic relapse or start of new therapy.

After the end of study treatment, all participants must be followed for adverse events (AEs) for 150 days following the last dose of sabatolimab, or 30 days following the last dose of azacitidine, whichever is later. All participants who discontinued study treatment while in remission with absence of hematologic relapse will enter a long-term follow-up for efficacy as described in the study flow diagram below (Figure 3-2) and outlined in Section 9.1.

[figure not shown]
^{*} Criteria to proceed with sabatolimab dose increase or Go/No Go for Cohort 2: based on DLTs during the first 2 cycles of study treatment in Cohort 1.

^{**} Go criteria for potential expansion monotherapy cohort, combination cohort and adolescent cohort at the recommended dose for expansion determined by Safety Run-in: Based on an overall assessment of all available data, including safety, preliminary response assessment, clinical pharmacology, tolerability, and recommendations from participating investigators

R: participants will be randomized to Cohort 3 or Cohort 4

Study flow

Figure 3-2 Study Flow

*All participants will enter safety follow-up. After completion of the treatment period, all participants who discontinued study treatment while in remission with no evidence of hematologic relapse will enter post-treatment follow-up until hematologic relapse or start of new therapy. Additionally, participants with MRD- status at end of treatment will continue to be assessed for MRD until MRD+ or for 12 months after end of study treatment, whichever is earlier.

The study flow is comprised of 4 periods (Figure 3-2): prescreening, pretreatment (Screening), treatment, and follow up.

Participants will undergo safety assessments during screening and periodically during treatment and follow-up as outlined in Table 8-1 and Table 8-2.

An end of treatment visit will be performed when participants permanently discontinue study treatment. participants will then enter safety/post-treatment follow-up as shown in Figure 3-2 (see also Section 9.1.1).

Based on safety and efficacy in previous cohorts, option, via protocol amendment, for expansion cohorts or additional treatment cohorts combining sabatolimab with e.g. donor lymphocyte infusions (DLI) or other novel combinations will be considered.

4 Rationale

